3.0 Objectives

The objective of this study is to test the potential effectiveness of 600 Hz sacral root stimulation to limit urethral sphincter activity in individuals with neurogenic bladder dysfunction (Aim 1). We hypothesize that sacral root stimulation at 600 Hz will result in lower urethral sphincter pressures compared to pressures in response to stimulation at the lower frequencies that are typically used for SARS. We will also test if this stimulation similarly limits anal sphincter activity (Aim 2). Individuals will already have received an implanted SARS device and will have also received a rhizotomy.

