5.0 Study Procedures

5.1 Study Design

In this 2-year case series study, we will enroll 8 participants, male or female, who have SCI and who already use implanted sacral root anterior stimulation to manage their bladder. Participants will act as their own controls.

If a participant is a Veteran, then they will complete study visits at the Cleveland VA Medical Center. If they are not a Veteran, then they will complete study visits at MetroHealth Medical Center for which we already have an approved IRB protocol.

During an initial study visit, expected to take about one hour, we will obtain informed consent. Then a sample of urine will be collected and tested to determine if they have a urinary tract infection.

In the days following this initial visit, subjects will be prescribed an antibiotic, which they will pick up from Pharmacy, to take in the days before and after participation in this study to prevent a urinary tract infection. We will contact subjects in the days leading up to the second visit to remind them of the antibiotic.

A second study visit will then occur 2-30 days later and last about 4 hours. Stimulus waveforms for urethral sphincter inhibition will be tested in the clinical laboratory in a single session. We will not need to conduct new surgeries or implant procedures. The primary outcome measure is urethral sphincter pressure, and additional outcome measures include bladder pressure, rectal pressure, and bladder volume as measured in clinically standard urodynamics examination. The primary outcome measure for Aim 2 is anal sphincter pressure.

Clinical Impact

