This study represents the first attempt to limit urethral sphincter contraction via 600 Hz stimulation of sacral roots in human participants. This approach using 600 Hz sacral root stimulation has successfully demonstrated voiding in chronic spinalized dogs, but has not been tested in humans. The Finetech-Brindley external controller has been modified to be capable of producing stimulation up to 600Hz. An Investigational Device Exemption has been obtained from the FDA to test this approach in human participants. Thus, one significant advantage of our study is that we will use this modified external controller to communicate with the already-implanted components of the system without new surgical procedures or significant risks. A second key advantage is that, because they have had a posterior rhizotomy, we can determine the stimulation parameters for activating and potentially limiting sphincter activity directly via the motor nerves, without confounding effects from sacral spinal reflexes. If this project is successful, these parameters can be applied in a future project to individuals who can have a stimulator implanted without rhizotomy, to determine if reflex activation of the sphincter can also be reduced. We understand that future work without rhizotomy will include the influence of reflex pathways, and this study may help us understand that influence by having this negative control. A future project would also then refine this approach by combining 600 Hz stimulation to reduce sphincter pressure with 20 Hz stimulation to evoke bladder contraction.

This project could have a high impact for individuals with neurogenic bladder dysfunction. It would help to address one of the highest priorities of individuals with SCI – restoration of bladder function - and help to address some of the biggest costs and health risks associated with managing neurogenic bladder by potentially improving bladder emptying without the need for catheters. There is a high potential for clinical translation because this approach takes advantage of existing technologies.

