If this project demonstrates evidence of urethral sphincter pressure reduction in response to 600 Hz stimulation, then we will propose in a subsequent project to apply 600 Hz stimulation to individuals with SCI in whom sacral reflexes are intact. We would implant a SARS device without the rhizotomy, and determine if reflex contractions of the sphincter can be prevented during bladder emptying. In this way, we plan to achieve efficient, catheter-free, on-demand bladder emptying using sacral root stimulation without the need for a posterior rhizotomy.

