5.5 Study Evaluations

We will use standard clinical urodynamics methods for data collection. We will use an FDA-approved modified external controller to communicate with the already-implanted components of the system, so no new surgeries or other procedures are required. The device has been modified to achieve frequencies up to 600 Hz and this modification was approved by the FDA in an IDE. We will document their normal daily usage device settings for reference, including stimulation amplitude, pulse width, frequency, and on/off cycle duration.

Clinical Urodynamics and Anorectal Manometry Procedure: A standard catheter will be inserted into the bladder via the urethra and the bladder will be emptied. This catheter will be removed and then a second catheter, which can measure bladder and urethral pressures, will be inserted. This catheter will also have a lumen for filling the bladder with sterile saline. A balloon catheter inserted in the rectum will be used to reflect abdominal pressure and distinguish bladder pressures due to detrusor contraction versus bladder pressures due to abdominal activity. This balloon catheter will measure rectal pressure. It will also have pressure transducers at the anal sphincter to measure anal sphincter pressure. Surface electromyogram (EMG) electrodes will be applied to the anal sphincter to monitor pelvic floor muscle contractions. Infused volumes will be controlled via an infusion pump. EMG and pressure signals will be monitored on a clinical urodynamic system. The participant's bladder will be infused with sterile saline while measuring bladder, urethral sphincter, and rectal pressures.

Sacral Anterior Root Stimulation: We will set the stimulation parameters for the implanted stimulator, including stimulation amplitude and frequency, using a modified Finetech-Brindley external controller unit. The frequency will be set either to 600 Hz or to the low frequency that the participant typically uses for emptying their bladder, which is usually 20 Hz. We will use the participant's own power transmission coil. The receiver coil and electrodes will already have been implanted. The pulse width will not be changed from the participant's normal setting.

Aim 1: Determine if 600 Hz sacral root stimulation limits contraction of the urethral sphincter.

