During visit 2, in a single session, we will first administer SARS using the stimulation parameters (i.e., frequency, pulse width, and amplitude) that the study participant typically uses to empty their bladder and has been for years. The purpose is to characterize the usual level of urethral sphincter and bladder pressure during their bladder emptying routines and collect these baseline data.

We will also have a frame of reference for stimulation amplitude for testing 600 Hz stimulation.

We will then decrease the stimulation amplitude and identify the threshold amplitude to achieve urethral sphincter contraction at low frequency, which will be compared to the threshold amplitude to evoke bladder contraction. The motor efferents innervating the urethral sphincter are significantly larger in diameter than the motor efferents innervating the bladder, so the thresholds for activating the bladder are higher than for activating the urethral sphincter. These thresholds amplitudes at low frequency will give us additional context for evaluating the recruitment of urethral sphincter and bladder pressures in response to sacral stimulation.

We will then test stimulation at 600 Hz. 600 Hz stimulation will first evoke a brief (~1-2 second) onset respond and then the urethral pressure is expected to return to baseline. The stimulation amplitude will be set to 0 mA and gradually increased to determine the threshold amplitude for evoking an initial onset response of the urethral sphincter. We will continue to increase the stimulation amplitude until we have achieved maximal urethral sphincter pressure onset response. Stimulation will be maintained for up to 10 seconds with at least 30 seconds rest between stimuli. Once this recruitment curve is established, we will repeat stimulation at threshold, 50% maximal recruitment, and 90% maximal recruitment for up to 30 seconds to measure reduction of urethral sphincter pressures.

Aim 2: Determine if 600 Hz sacral root stimulation limits contraction of the anal sphincter.

This aim has the same design as Aim 1 but will focus on bowel function. Data for this aim will be measured during the same session as Aim 1. We will administer SARS using the stimulation parameters and pattern that the participant typically uses to empty their bowel and has been for years. These data will give us context for evaluating effects on bowel function.

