5.6 Data Analysis

Outcomes from urodynamics data will be used to determine the effect of electrical stimulation on limiting urethral and anal sphincter pressures. Distributions of pressures without and with 600 Hz and 20 Hz stimulation will be compared with an ANOVA and a significance level of 0.05. We expect to observe a lower level of urethral and anal sphincter pressure in response to sacral stimulation at frequencies of 600 Hz compared to the low stimulation frequency that participants typically use.

Potential Limitations and Alternative Solutions

If 600Hz sacral stimulation in humans fails to limit urethral and anal sphincter activity compared to what is evoked at low frequency, then we will need to consider alternative stimulation strategies in future studies. We acknowledge that another potential approach using kilohertz frequency stimulation could be considered. Our group and others have tested kilohertz frequency sinusoidal waveforms extensively preclinically to block nerve conduction. This could be another alternative to the rhizotomy, but it would require development and regulatory approval of a new implantable stimulation system that can safely deliver stimulation in the kilohertz frequency range for human testing [14]– [18].

We do not expect to experience significant technical challenges because (1) we are using a SARS system that study participants have been successfully using for years and (2) we are using research methods that we have successfully used for years to collect these data [19], [20]. We may find that the external controller does not deliver sufficient charge to achieve sphincter reduction at elevated stimulation frequencies. This is unlikely because the amplitude required to avoid contraction at 600Hz frequencies is not significantly higher than the amplitude to achieve activation at lower amplitudes.

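### Section 5.6 compares 600 Hz with the usual low frequency without using the onset response, so weaker recruitment at 600 Hz can look like limited contraction

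*Combined protocol and SAP*

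**What the plan says.** Section 3.0 hypothesises that "sacral root stimulation at 600 Hz will result in lower urethral sphincter pressures compared to pressures in response to stimulation at the lower frequencies" usual for this implant. Section 5.6 gives the analysis in one sentence: "Distributions of pressures without and with 600 Hz and 20 Hz stimulation will be compared with an ANOVA and a significance level of 0.05". The direction it expects is "We expect to observe a lower level of urethral and anal sphincter pressure in response to sacral stimulation at frequencies of 600 Hz" than at the usual low frequency.

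Section 5.5 sets out the recordings:

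- One frequency is delivered at a time: "The frequency will be set either to 600 Hz or to the low frequency that the participant typically uses for emptying their bladder".
- The low-frequency baseline is recorded at the participant's own emptying settings. A later step lowers the amplitude to find the low-frequency thresholds.
- The 600 Hz amplitude is raised from 0 mA until an onset response appears, and then until that response is maximal. Holds of up to 30 seconds follow at threshold, 50% and 90% of maximal recruitment.
- The onset response is expected to last about 1 to 2 seconds, and "then the urethral pressure is expected to return to baseline".
- Aim 2 repeats the design for the anal sphincter.

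Under Clinical Impact, section 5.1 leaves "combining 600 Hz stimulation to reduce sphincter pressure with 20 Hz stimulation to evoke bladder contraction" to a future project. Its go statement begins "If this project demonstrates evidence of urethral sphincter pressure reduction in response to 600 Hz stimulation" and leads to a proposal to implant the device without rhizotomy.

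**The concern.** Aim 1 asks whether 600 Hz limits contraction. Every participant has had a rhizotomy and 600 Hz is given alone, so after the brief onset there is no other sacral drive for it to suppress. The best expected result is baseline pressure. A stimulus that barely recruits the sphincter also leaves pressure near baseline. Low-frequency stimulation at the emptying amplitude does contract the sphincter. Both explanations therefore predict the same direction in 5.6.

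The ANOVA's no-stimulation condition does not separate them, since both put 600 Hz close to rest. The limitations text in 5.6 shows that the ambiguity was not noticed. It lists insufficient charge as a reason why reduction might not be seen, whereas on the stated contrast weak delivery would push the result towards apparent success.

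At stake is what the result can be said to mean, and how firmly it supports the next step described in 5.1.

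**Working it through.** The plan gives no effect size, SD or pressure, so there is no figure to reproduce. The check is algebraic, with an illustration on assumed values.

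**Set-up.** Let A be the pressure rise above baseline at full sphincter recruitment, *r* the fraction recruited, and *s* the fraction of the rise that persists after onset. Assume that the onset rise is *rA*, that the later rise is *rsA*, and that A is the same at both frequencies. The frequency effect of interest is *s* at 600 Hz being smaller than *s* at low frequency.

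**What 5.6 compares.** Later pressure at 600 Hz minus later pressure at low frequency is A(r₆₀₀s₆₀₀ − r_LF s_LF). It is negative if s₆₀₀ < s_LF, and also if r₆₀₀ < r_LF with no difference in *s*. The sign alone cannot say which.

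**Size when frequency has no effect (s₆₀₀ = s_LF).** Relative to the low-frequency rise, the difference is r₆₀₀/r_LF − 1.

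Inputs:

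- r₆₀₀ = 0.5 and 0.9 for the two upper holds (section 5.5).
- r₆₀₀ at threshold: assumed 0 to 0.1. The documents give no value.
- r_LF at the usual emptying amplitude: assumed 0.7 to 1. The documents give no value, but 5.5 says that the sphincter is activated at lower amplitudes than the bladder, so an amplitude that empties the bladder should recruit much of the sphincter.

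| 600 Hz holds used | Mean r₆₀₀ | r_LF = 1 | r_LF = 0.7 |
|---|---|---|---|
| Threshold only | 0 to 0.1 | −100% to −90% | −100% to −86% |
| 50% only | 0.5 | −50% | −29% |
| 90% only | 0.9 | −10% | +29% |
| All three pooled | (0 + 0.5 + 0.9)/3 = 0.467 to (0.1 + 0.5 + 0.9)/3 = 0.5 | −53% to −50% | −33% to −29% |
| 50% and 90% pooled | (0.5 + 0.9)/2 = 0.7 | −30% | 0% |

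On these assumptions, pooling all three holds produces an apparent reduction of 29% to 53% from recruitment alone. Dropping the threshold holds cuts this to between 0% and 30%. It does not remove it, because the amplitudes are still not matched.

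**What removes it.** Within a run, later rise divided by onset rise is rsA/(rA) = s. Recruitment cancels. Computing the same quantity in the low-frequency recordings and comparing it within participant addresses frequency rather than recruitment. It needs a clear onset rise in the denominator, which is a second reason to keep threshold holds out.

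**Windows.** A selected onset maximum tends to exceed a later average through ordinary fluctuation, even when contraction is fully sustained. Means over fixed windows avoid that.

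**The case against.** The strongest reply is that the procedures already guard against a stimulus that does nothing. The 600 Hz amplitude is set by the onset response, and the holds are run only once a recruitment curve exists. A stimulus that never recruited would have no threshold, 50% or 90% level and would yield no hold data. This stands. Threshold is also, by definition, an amplitude that evokes some response, so it is not inert.

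A reader might go further and infer that a non-recruiting 600 Hz stimulus would pass as a success and trigger the next study. The documents do not support that. The titration would expose such a stimulus, and the go statement in 5.1 speaks of evidence of pressure reduction without tying it to the ANOVA. The fall from onset to baseline described in 5.5 could count as such evidence.

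It is also fair that the hypothesis in 3.0 is comparative and that the contrast tests it, and that 5.1 openly defers combined stimulation. None of this closes the gap in 5.6. The onset response is a procedural step only. The analysis names no time window, no recruitment condition and no rule on which amplitudes enter.

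**Conclusion.** The concern holds in a limited form and should be fixed before analysis. The 5.6 contrast can support the statement that sustained pressure was lower at 600 Hz than at the usual low frequency. It cannot alone support the statement that 600 Hz limits contraction, because unequal recruitment gives the same direction and threshold holds may be set against the full usual amplitude.

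That logic needs no numerical assumption. The 29% to 53% figure does. It rests on assumed recruitment fractions, on pressure rising in proportion to recruitment, and on the same maximal rise at both frequencies. It illustrates scale and does not predict this trial's result. If the usual amplitude recruits the sphincter less fully than assumed, the bias shrinks and can reverse.

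**What to change.** Amend 5.6 for both aims before any data are analysed:

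1. Base the confirmatory comparison on the 50% and 90% holds with a documented onset response in the sphincter concerned, classed by that sphincter's own recruitment curve. Report threshold holds descriptively.
2. In each 600 Hz run, take mean pressure in a fixed onset window (for example the first 2 seconds) and in a fixed later window, each minus pre-stimulus baseline. Use window means, not a selected peak. Compute the same later-to-onset measure in the low-frequency recordings and compare the two frequencies within participant. Where the usual low-frequency setting cycles on and off, both windows should lie within one on period. If that is not possible, say so.
3. Report later-window pressure minus baseline at 600 Hz with a 95% CI, next to the difference between 600 Hz and low frequency, and note that the amplitudes are not matched.
4. Word the 5.6 conclusion and the 5.1 go statement along these lines: *600 Hz recruits the sphincter but evokes less sustained pressure than low frequency; suppression of an ongoing contraction was not tested.*

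This uses recordings already planned and adds no stimulation, visits or participants. The cost is a narrower claim and fewer holds in the confirmatory comparison.

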5.7 Withdrawal of Subjects

There may be instances that would require investigators to terminate a participant's participation in this study. Investigators will stop the experiment if the participant demonstrates any unresolved physical or psychological discomfort.

6.0 Risks

Tissue Damage – rare. There is a small risk that the neural tissue may be damaged by the application of electrical stimulation. This risk will be minimized by applying stimulation within amplitude and duration parameters that were safe and effective in chronic preclinical experiments.

Urinary tract infection: This risk is uncommon. There is a risk of less than 10% that a subject will develop a urinary tract infection (UTI) following urodynamics in this study. This risk will be minimized by performing catheterization with sterile technique and by taking antibiotics before and after the experiment as

prescribed. If a subject experiences signs or symptoms of a UTI (such as blood in the urine, frequency, urgency, increased spasms, fever, chills, and/or pain in the lower back) after the study, please contact a member of the study team. Subjects will be advised on how to proceed for medical treatment.

Urethral trauma: This risk is uncommon. There is a small risk, which we estimate at approximately 2%, that a subject will experience mild trauma to the urethra as a result of catheterization for this study. Such trauma might result in a small amount of bleeding from the surface of the urethra, similar to that seen from the gums on vigorous tooth-brushing. This risk will be minimized by lubricating the catheter with sterile water-soluble gel and by careful catheterization technique.

Discomfort during urodynamic testing: Subjects may experience some discomfort from lying down for up to four hours at a time during these procedures. If so, the investigators will assist subjects in changing position to become more comfortable. The investigators will assist subjects in changing position at least every 2 hours, if the procedures last that long, to reduce the risk of pressure injuries.

Reproductive Health/Sexual Activity: The effects on the developing child of using electrical stimulation during pregnancy and the risk of birth defects are unknown. Therefore, women who are pregnant or breastfeeding may not participate in this study.

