[1669332] High-frequency sacral root stimulation to improve bladder and bowel emptying following SCI

Funding Agency: Department of Veterans Affairs

Principal Investigator/Study Chair: [name]

Version 1.6
2 February 2023

Abstract

This is a 2-year case series study. Study participants will act as their own controls. This study will determine if sacral root stimulation at 600 Hz limits urethral sphincter contractions in individuals with SCI who have already been implanted with a Finetech-Brindley SARS system. The Finetech-Brindley SARS system is an FDA-approved device (Humanitarian Use Device) and we have received an IDE for testing this device at 600 Hz. In an initial visit lasting about 1 hour, we will complete an informed consent process to enroll the participant and collect a urine sample to test for a UTI. In a second visit lasting about 4 hours, we will conduct experiment procedures. Bladder and urethral sphincter pressures will be recorded using standard clinical urodynamics techniques. In a urodynamics laboratory, we will collect baseline data in response to the typical stimulation parameters that the participant uses for their daily bladder management. We will then test 600 Hz stimulation to determine whether this results in reduced sphincter contraction (Aim 1). The Finetech-Brindley device can also be programmed to achieve bowel emptying and return of bowel control is an extremely high priority for individuals with SCI [7]. Therefore, we will leverage the opportunity of this pilot study to determine if 600 Hz sacral root stimulation also has the potential to improve bowel emptying by reducing anal sphincter pressure (Aim 2). Participants will be asked to participate in experiments for both Aim 1 and Aim 2. Study participants who are Veterans will be consented and tested at the Cleveland VA Medical Center. Participants who are not Veterans will be consented and tested at the MetroHealth Medical Center. An IRB protocol for this study has already been approved at the MetroHealth Medical Center.

List of Abbreviations

CRC – Clinical Research Center
DSD – detrusor-sphincter dyssynergia
FES – functional electrical stimulation
LSCVAMC – Louis Stokes Cleveland Department of Veterans Affairs Medical Center
NIDDK - National Institute of Diabetes and Digestive and Kidney
NIH – National Institute of Health
SARS - sacral anterior root stimulation
SCI - spinal cord injury
SCI&D - Spinal Cord Injury & Dysfunction
TDL - Technical Development Laboratory

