We will then test stimulation at 600 Hz. This testing can be done simultaneously with 600 Hz testing for Aim 1. The stimulation amplitude will be set to 0 mA and gradually increased to determine the threshold amplitude for evoking an initial onset response of the anal sphincter. We will continue to increase the stimulation amplitude until we have achieved maximal anal sphincter pressure onset response. Stimulation will be maintained for up to 10 seconds with at least 30 seconds rest between stimuli. Once this recruitment curve is established, we will repeat stimulation at threshold, 50% maximal recruitment, and 90% maximal recruitment for up to 30 seconds to measure reduction of anal sphincter pressures.

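### Neural damage is a named (rare) risk of this first human 600 Hz study, yet no study-initiated contact follows visit 2 and usual settings are not retested after the last 600 Hz run

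*Combined protocol and SAP*

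**What the plan says.** **Risk.** Section 6.0 states: "There is a small risk that the neural tissue may be damaged by the application of electrical stimulation". The stated protection is to stay within amplitudes and durations found safe in chronic preclinical work. Section 5.1, under Clinical Impact, states: "This study represents the first attempt to limit urethral sphincter contraction via 600 Hz stimulation of sacral roots in human participants".

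**Contacts.** Section 5.1 sets out two visits. The study-initiated contact it describes comes before visit 2: "We will contact subjects in the days leading up to the second visit to remind them of the antibiotic". Section 6.0 gives a route after the study that the participant must start. It opens "If a subject experiences signs or symptoms of a UTI" and lists infection symptoms, including blood in the urine.

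**Order within visit 2 (section 5.5).** Aim 1 begins with the participant's usual settings, then low-frequency thresholds, then the 600 Hz recruitment curve, and ends with 600 Hz repeats of up to 30 seconds. For Aim 2 the protocol says "We will administer SARS using the stimulation parameters and pattern that the participant typically uses to empty their bowel", and the 600 Hz steps come after that. Of the Aim 2 600 Hz runs it says: "This testing can be done simultaneously with 600 Hz testing for Aim 1".

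**Monitoring and reporting.** Pressures are recorded throughout, and "Surface electromyogram (EMG) electrodes will be applied to the anal sphincter to monitor pelvic floor muscle contractions". Section 5.7 stops the experiment for unresolved discomfort. Section 7.0 makes participant safety the primary concern and provides for adverse event review through VA channels. Section 9.0 commits to reporting to oversight bodies, including both IRBs.

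**The concern.** The protocol names a harm to the nerves through which the implant works, and describes how to prevent it but not how to find out whether it has happened. Participants depend on this device: the Abstract refers to "the typical stimulation parameters that the participant uses for their daily bladder management". A lasting fall in response would therefore matter to them directly.

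The discomfort-based stop in section 5.7 may be an insensitive signal here. Every participant has had a rhizotomy, which section 2.0 says impairs sacral sensation where it is present. The in-session recordings at 600 Hz are also hard to read as a safety check, because a fall in sphincter pressure is the intended effect. Without a return to usual settings, a low reading cannot readily be separated from a lost response.

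The team also plans a follow-on project with new implants and no rhizotomy (section 5.1). A uniform record of how participants' devices worked after exposure would help with that step. Relying on participants to volunteer a change gives each of them a different chance of being counted.

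**Working it through.** The plan gives no figure to reproduce on this point. The check is a trace of the schedule, with short arithmetic for cost and context.

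**1. Is usual stimulation retested after 600 Hz?**

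| Step in section 5.5 | Setting |
|---|---|
| Aim 1 baseline and thresholds | usual, low frequency |
| Aim 1 recruitment curve and repeats | 600 Hz |
| Aim 2 context stimulation | usual bowel settings |
| Aim 2 recruitment curve and repeats | 600 Hz |

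Run in this order, the usual bowel stimulation follows the Aim 1 exposure, so some low-frequency response is seen after 600 Hz. It still precedes the Aim 2 exposure, and its stated purpose is context for bowel function. If the two sets of 600 Hz runs are done together, even that partial check may disappear. In either case, nothing is described after the last 600 Hz run.

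**2. Is there contact afterwards?** Study-initiated contacts after visit 2: 0 for each of 8 participants. Participant-initiated routes: one, for infection symptoms. The consent form also carries team contact details, for questions during the study (section 5.3). Section 5.2 mentions regular follow-up about the implant, but in the context of recruitment and with no timing tied to visit 2.

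**3. Cost of one call each.** Assumed 10 to 15 minutes per call: 8 × 10 = 80 and 8 × 15 = 120 minutes for the whole study.

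**4. Other after-effects the call would cover.** Section 6.0 gives UTI at under 10% and urethral trauma at about 2% per participant. Treating participants as independent, the chance of at least one event among 8 is:

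- UTI: below 1 − 0.90^8 = 0.570, so under 57%.
- Urethral trauma: 1 − 0.98^8 = 0.149, about 15%.

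These figures concern other risks. They show that the call has further use, not how likely nerve damage is.

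**5. Cost of the optional in-session repeat.** Assumed 10 to 15 minutes of rest plus 2 to 5 minutes at usual settings: 10 + 2 = 12 and 15 + 5 = 20 minutes. As a share of a 240-minute visit, 12/240 = 5.0% and 20/240 = 8.3%.

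**6. What eight clean answers would show.** The one-sided 95% upper limit for 0 events in 8 is 1 − 0.05^(1/8) = 0.312. Only true rates above about 31% would be excluded. The benefit is detection in each participant, not an estimate of a rate.

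**The case against.** The case against has real weight.

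- **Existing safeguards are substantial.** Participants use the stimulator daily, so its function at usual settings is tested in ordinary life soon after the session. Clinical staff already make regular contact about the device. Pulse width stays at the participant's normal setting, amplitude is ramped from 0 mA, runs are short, and the modified controller is used under an FDA device exemption. This stands, and it makes an unnoticed marked loss unlikely.
- **One call is a limited detector.** A change too small to notice will not surface when asked about, a temporary one depends on recall, and one arising after the call is missed. This also stands. The call mainly catches changes that were noticed but not volunteered. The in-session repeat is the only objective check for partial loss, and an acute change there may be fatigue.
- **Follow-up may be required elsewhere.** The device-exemption conditions, the consent form, the MetroHealth protocol for non-Veterans, and the personnel and resources sections (1.0 and 4.0 in the contents list) were not available. The point is therefore limited to the text that was.

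Three stronger readings are tempting, and the documents do not support them. A reader might infer that participants have no route to the team after visit 2, but section 6.0 gives one for infection symptoms. A reader might infer that adverse events are reviewed only when volunteered, but section 7.0 does not say so: it uses ordinary reporting language, sets no collection window, and is supplemented by section 9.0. A reader might infer that 600 Hz stimulation is likely to cause damage here, but the protocol calls the risk rare and gives no rate.

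**Conclusion.** The point holds as a modest gap in safety ascertainment. A named risk, in first human use at this frequency, has a preventive step but no planned detection step after the last exposure. Study-initiated contacts after visit 2 number 0 for each of 8 participants, and the participant-initiated route does not mention loss of stimulator response.

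What could be missed is mainly a change that the participant notices but does not report, or does not connect with the session. A partial loss too small to notice could also pass undetected. The size of the underlying risk cannot be stated, because the documents give no rate for nerve damage. The primary outcome and its analysis are unaffected. The change is worth making because it is cheap. The conclusion rests on the available text; the minutes quoted for calls and for the repeat are assumptions.

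**What to change.** 1. **Sections 5.1 and 6.0:** add one scheduled telephone contact about one week after visit 2. Ask whether the usual settings still empty the bladder and the bowel as before, and ask about UTI symptoms or bleeding. Record every answer, including a negative one. Send any reported loss to a clinical device check and to the reporting channels in section 7.0.
2. **Section 6.0:** tell participants to report any loss of response to their stimulator, alongside the UTI symptoms already listed.
3. **Section 5.5, where session time allows:** after a rest following the last 600 Hz run, repeat the usual low-frequency stimulation once and compare it with the baseline from the start of the session. State that an acute change may be fatigue and does not by itself show damage.
4. If the device-exemption conditions, the consent form or the MetroHealth protocol already require such follow-up, carry it into this protocol.

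**Cost.** Items 1 and 2 take 80 to 120 staff minutes in total (assumed) and a few sentences of text, with no new procedure. Item 3 adds an assumed 12 to 20 minutes of lying down per participant. Section 6.0 already notes discomfort and pressure-injury risk from the long session, so item 3 is optional.
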